Treatment related Lymphocytosis: Similar to other agents targeting B-cell receptor signaling, transient lymphocytosis is a pharmacodynamic effect of ibrutinib, in which the inhibition of BTK-mediated cellular homing and adhesion results in a mobilization of tumor cells to the peripheral blood (Stevenson 2011).

A reversible increase in lymphocyte counts (ie, $\geq 50\%$ increase from baseline and above absolute count 5000/mcL), often associated with reduction of lymphadenopathy, has been observed in most subjects (approximately 69% to 75%) with CLL/SLL treated with single agent ibrutinib. This effect has also been observed in some subjects (33%) with MCL treated with single agent ibrutinib. This observed lymphocytosis is a pharmacodynamic effect and should not be considered progressive disease in the absence of other clinical findings. In both disease types, lymphocytosis typically occurs during the first few weeks of ibrutinib therapy (median time 1.1 weeks) and typically resolves within a median of 8.0 weeks in subjects with MCL and 18.7 weeks in subjects with CLL/SLL.

Lymphocytosis appeared to occur in lower incidence and at lesser magnitude in subjects with CLL/SLL receiving ibrutinib in combination with chemoimmunotherapy (ie, 27% of subjects receiving ibrutinib + BR in Study 1108) or immunotherapy (ie, 55% of subjects receiving ibrutinib + ofatumumab in Group 2 of Study 1109). A substantial increase in the number of circulating lymphocytes (e.g., $> 400,000/\mu\text{L}$) has been observed in a subset of subjects. There have been isolated cases of leukostasis reported in subjects treated with ibrutinib.

Bleeding-related events: There have been reports of hemorrhagic events in subjects treated with ibrutinib both with and without thrombocytopenia. These include primarily minor hemorrhagic events such as contusion, epistaxis, and petechiae; and some major hemorrhagic events including gastrointestinal bleeding, intracranial hemorrhage and hematuria.

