11.0 Treatment Evaluation/Measurement of Effect

Formal response evaluation should occur every 3 treatment cycles as per standard clinical practice. However, first response evaluation will occur at the end of 4 treatments of daratumumab (completion of cycle 1). This will allow correlation of the clinical activity of the single agent daratumumab with the correlative studies planned. Thereafter the clinical response will be evaluated after completion of every 3 cycles during combination therapy. Objective status should be classified as PD vs. Not PD on cycles when a formal response evaluation does not occur.

Patients will also be assessed as MRD^+ vs MRD^- (See section 11.4). Prior to the response evaluation (after 3 cycles of the combination), baseline on study measurements will be used to determine disease progression (e.g. not cycle by cycle comparisons). Once patients undergo formal response evaluation, the nadir value at either baseline or time of response evaluation will be used for evaluating future disease progression. In addition to a baseline scan, confirmatory scans should also be obtained as needed to document objective response at sites of non-palpable lymphadenopathy or organomegaly as indicated in Section 4 or as needed clinically.

NOTE: Information from CT scans is not considered in the standard classification of response.

Note: Treatment-related lymphocytosis is a known phenomenon with ibrutinib and is not representative of PD. As noted in the Leukemia Research Foundation Workshop report⁶²: "Patients with lymphocytosis and no other evidence of PD should continue therapy until they develop other definitive signs of PD (i.e., at least one feature suggesting worsening of the CLL other than lymphocytosis (e.g., anemia, thrombocytopenia, lymphadenopathy, or hepatosplenomegaly) or the occurrence of another reason to discontinue therapy."

PD: "If PD is suspected, clinical examination, computed tomography, and peripheral blood counts should be obtained, and a bone marrow biopsy considered, to provide objective assessment of CLL status. Similarly, persistent lymphocytosis should not interfere with the time of designation of a PR, which should be based more on the other measurable aspects of the disease than on lymphocytosis."

11.1 Schedule of Evaluations:

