NOTE: In a patient who achieves clinical and laboratory evidence of a complete response, the objective status should be recorded as a CCR on the cycle where the formal response evaluation occurred until a bone marrow biopsy and aspirate have been performed. At that time, the objective status should be amended to classify the patient as a CR, CRi, or nPR **on the cycle where the formal response evaluation occurred**.

11.216 Patients who have clinical and laboratory evidence of CR but who have not yet had a bone marrow biopsy to distinguish between CR and nPR will be classified as having a **Complete Clinical Response (CCR)** until the marrow biopsy is obtained. Patients must meet all of the blood count parameters listed in section 11.214.

11.217 In some settings MRD assays may be considered as a surrogate of response as discussed in section 11.3. No other laboratory assays (e.g., quantitative immunoglobulins) will be used currently as an index for response but will be recorded for clinical correlations.

11.218 For patients whose only measurable disease at the time of enrollment is on CT scan (i.e. SLL with no palpable nodes), a CT scan showing absence of lymphadenopathy (e.g. lymph nodes >1.5 cm) is required before classifying patients a CR.

11.22 **PARTIAL RESPONSE (PR)** requires the patient exhibits at least two of the features in Sections 11.221, 11.222, and 11.223 below (if abnormal prior to therapy) as well as one or more of the remaining features (Sections 11.224, 11.225, 11.226) for at least 2 months. In addition to the parameters listed below, the presence or absence of constitutional symptoms will be recorded.

11.221 $\geq 50\%$ decrease in peripheral blood lymphocyte count from the pretreatment baseline value. Note: This criteria will not be applicable if patients are experiencing ibrutinib associated lymphocytosis as noted above in section 11.0. (LRF workshop)⁶²

11.222 $\geq 50\%$ reduction in the sum of the products of the maximal perpendicular diameters of the largest measured node or nodal masses in the right and left cervical, axillary, and inguinal lymph node regions on physical examination.

11.223 $\geq 50\%$ reduction in size of liver and/or spleen as measured by physical exam noting the maximal distance below the respective costal margins of palpable hepatosplenomegaly during rest.

11.224 Neutrophils $>1500/\mu\text{l}$ or 50% improvement over baseline.

11.225 Platelets $>100,000/\mu\text{l}$ or 50% increase over baseline.

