11.24 **STABLE DISEASE (SD):** Patients who do not meet criteria for CR, CRi, nPR, CCR, PR, or PD will be classified as having "stable disease".

11.25 **Not PD:** The patient was evaluated for progression only this cycle and a formal response evaluation did not occur. The patient did not meet the criteria for progression per section 11.23.

Note: Formal response evaluation should occur every 2 cycles during treatment, with the first response evaluation occurring at the end of cycle 1. Formal response evaluation should occur at the end of treatment. Objective status should be classified as PD vs. Not PD on cycles when a formal response evaluation does not occur.

11.3 **EVALUATION OF MINIMAL RESIDUAL DISEASE (MRD):**
MRD will be assessed by flow cytometry in the bone marrow.

MRD definition

Patients will be considered MRD-negative when they have **bone marrow** less than one CLL cell per 10,000 leukocytes (or bone marrow consistent with $<0.01\%$ involvement). Patients will be recorded to have either MRD+vs. MRD⁻ disease.

A. **Baseline:** All patients will have MRD will be assessed on patients if their absolute lymphocyte count (ALS) in blood is $<5,000$ assessed by flow cytometry at baseline prior to initiation of therapy. This can be done either in the peripheral blood (PB) and/or the bone marrow aspirate (BM). (Note: If blood is **positive** for MRD then bone marrow aspirate analysis is not required for the clinical protocol, however if peripheral blood is **negative** then a bone marrow aspirate can be done to document MRD+ status of the patient as long as the bone marrow procedure is being considered as part of the standard of care for patient's disease management).

B. **On treatment:** All patients will have the MRD evaluated by flow cytometry on the peripheral blood **every 3 treatment cycles** while on maintenance therapy, with the first assessment occurring at the end of Cycle 4. MRD will first be done on the PB (to avoid excessive / unwarranted bone marrow biopsy procedure). If this is **positive**, then NO BM analysis will be required, but if the PB is **negative (on two consecutive evaluations at least 3 months apart)**, then a BM aspirate analysis for MRD will be done. If the ibrutinib/Daratumumab treatment is held ≥ 21 days for toxicity or for any other reason(s) then the MRD testing will be delayed to accommodate 3 treatment cycles prior to testing.

Methodology

We will employ Mayo Clinic Standard of care MRD assay.

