4. Nodular partial response (nPR) is essentially a patient who appeared to have a CR but nodules were present in the bone marrow. It requires fulfillment of all physical exam and lymphocyte criteria for CR; however, when the bone marrow is done to confirm CR, nodules of malignant lymphocytes are found. Patients must fulfill one or more of the blood count parameters (ANC, Platelets, Hemoglobin) but are not required to meet all 3 of these conditions. See Section 11.215 regarding the distinction between clonal and regenerative nodules.
5. Partial response (PR) requires fulfillment of at least two of the above-noted decrease in circulating lymphocytes, regression in adenopathy and regression in hepatosplenomegaly, and at least one other parameter listed above for a duration of ≥ 2 months. See Section 11.22.
6. Progression: Fulfilling the criteria as noted in section 11.23. Prior to the formal response evaluation, baseline on study measurements will be used to determine disease progression (e.g. not cycle by cycle comparisons). Once patients undergo formal response evaluation, the nadir value at either baseline or time of response will be used for evaluating future disease progression. In the absence of other indices of clinical progression, the presence of a ≥ 2 g/dL decrease in hemoglobin or a $\geq 50\%$ decrease in platelet count and/or absolute neutrophil count will not exclude a patient from continuing on the study. Although not mandatory, bone marrow aspirate and biopsy are strongly encouraged to better define the cause of the suppressed counts (e.g., treatment versus disease-related).

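### The partial-response rule keeps a count of two features when ibrutinib lymphocytosis removes one, conflicts with Section 11.0, and leaves some primary-endpoint classifications to the assessor

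*Combined protocol and SAP*

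**What the plan says.** - **PR rule (Section 11.22).** A PR "requires the patient exhibits at least two of the features in Sections 11.221, 11.222, and 11.223 below (if abnormal prior to therapy"). The three features are a lymphocyte fall (11.221), nodal shrinkage (11.222) and liver/spleen shrinkage (11.223). One of three blood-count features (11.224-11.226) is also needed, and the response must last at least two months.
- **Note to 11.221.** "This criteria will not be applicable if patients are experiencing ibrutinib associated lymphocytosis as noted above in section 11.0". Nothing says what then happens to the count of two.
- **Table 11.4, footnote 5.** A PR "requires fulfillment of at least two of the above-noted decrease in circulating lymphocytes, regression in adenopathy and regression in hepatosplenomegaly". The footnote has neither the baseline-abnormality clause nor a lymphocytosis exception.
- **Section 11.0.** A workshop report is quoted to the effect that "persistent lymphocytosis should not interfere with the time of designation of a PR". The sentence goes on to direct attention to the other measurable disease.
- **Section 11.24.** "Patients who do not meet criteria for CR, CRi, nPR, CCR, PR, or PD will be classified as having" stable disease.
- **Primary endpoint (Sections 16.11 and 16.311).** Success is CR, CRi, CCR, nPR or PR after six cycles of the combination.
- **Frequency and duration (Section 1.2).** Lymphocytosis occurs in 69-75% of CLL/SLL patients on ibrutinib alone, 55% with an added antibody and 27% with chemoimmunotherapy. Median onset is 1.1 weeks. It "typically resolves within a median of 8.0 weeks in subjects with MCL and 18.7 weeks in subjects with CLL/SLL". Section 9.4 adds that its occurrence after daratumumab is unknown.

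**The concern.** Consider a Rai I patient: lymphocytosis and enlarged nodes, with no palpable liver or spleen. If ibrutinib lymphocytosis is still present at the read-out, the nodal feature is the only one left to score. Two features cannot be shown however far the nodes shrink. CR, CCR, CRi and nPR are closed as well, because Table 11.4 requires lymphocytes below 4000/µL for each. The literal result is a non-response, while Section 11.0 points towards PR.

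This matters because PR counts as success in both cohorts and each cohort is judged against a fixed number of responders. In an open-label single-arm trial, two assessors could score the same patient differently and both cite the protocol. If the literal rule is followed, true responders are lost and an effective regimen may be declared ineffective. The read-out also falls close to the median resolution time, so the situation is foreseeable.

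**Working it through.** **1. The plan's own figures.** Exact binomial tails:
- Cohort 2, P(X ≥ 17 | n = 26): 0.0843 at p = 0.50 and 0.9091 at p = 0.75. The plan states 0.08 and 0.91.
- Cohort 1, P(X ≥ 3 | n = 22): 0.0948 at p = 0.05 and 0.8455 at p = 0.20. The plan states 0.09 and 0.85.

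Both designs reproduce. The arithmetic of the design is not at fault.

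**2. The Rai I patient under each text.**

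| Text | Result during lymphocytosis |
|---|---|
| 11.22 with the 11.221 note, literal | one feature available, two required: not PR |
| Table 11.4 footnote 5 | lymphocyte feature not met, one of three: not PR |
| 11.0 | lymphocytosis should not hold up PR; rely on other disease: PR possible |

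**3. Share still in lymphocytosis at the read-out.** Ibrutinib starts on Day 1 of Cycle 2, so the end of Cycle 7 (Section 16.11) is 6 × 4 = 24 weeks on drug. Assume exponential resolution with the 18.7-week median, counted from onset at 1.1 weeks:

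U = 0.5^((24 − 1.1)/18.7) = 0.428

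**4. Share affected.** m = incidence × U × N, where N is the share without baseline liver or spleen enlargement. The documents do not give N; 0.3-0.7 is assumed. Assume also that responders are affected in the same proportion as all patients. The recorded response rate is then 0.75 × (1 − m).

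| Incidence | In lymphocytosis | m (N = 0.3 to 0.7) | Recorded rate | Cohort 2 power |
|---|---|---|---|---|
| 27% | 11.6% | 3.5-8.1% | 72.4-68.9% | 0.846-0.732 |
| 55% | 23.5% | 7.1-16.5% | 69.7-62.6% | 0.760-0.473 |
| 69% | 29.5% | 8.9-20.7% | 68.4-59.5% | 0.710-0.345 |
| 75% | 32.1% | 9.6-22.5% | 67.8-58.1% | 0.688-0.295 |

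If the 18.7 weeks run from the start of ibrutinib, U = 0.5^(24/18.7) = 0.411, m is 3.3-21.6% and power is 0.849-0.319.

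**5. Cohort 1.** With the same m of 3.5-22.5%, 0.20 × (1 − m) is 0.193-0.155, and power falls from 0.85 to 0.83-0.69. Patients allowed to start ibrutinib in Cycle 1 have a different time on drug, so this is only indicative.

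**6. Earlier read-out.** Section 16.311 says end of cycle 6, which is 20 weeks on ibrutinib. U = 0.5^(18.9/18.7) = 0.496, m = 4.0-26.1%, and Cohort 2 power is 0.83-0.21. If the two-month duration must be completed by the read-out, the features are needed earlier still and exposure rises.

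**7. The null.** Section 16.22 cites a 54% response rate at 8 months for ibrutinib alone before setting the 50% null. If that study scored strictly and the same m applied, the equivalent null under the relaxed rule is 0.50/(1 − m) = 0.518-0.645. Then P(X ≥ 17 | 26) = 0.12-0.55, against the stated 0.08. Fewer patients should still be in lymphocytosis at 8 months, so the upper end probably overstates this.

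**The case against.** A reader might infer that the plan scores every node-only responder as stable disease. The documents do not support that, for these reasons:

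- **Section 11.0 supports PR.** The 11.221 note refers back to 11.0 and cites the same workshop report, so it can be read as applying that principle.
- **The note does not create the obstacle.** Section 1.2 describes ibrutinib lymphocytosis as a rise of at least 50% from baseline. Such a patient could not show a 50% fall with or without the note, so the note arguably has a purpose only if it relaxes the rule.
- **Stable disease is not the only literal outcome.** Section 11.234 counts a 50% lymphocyte rise to at least 5000/mm³ as progression and exempts infection and tumor flare, not ibrutinib. Read just as literally, some of these patients would be progressions.
- **The group is narrow.** It consists of patients still in lymphocytosis at the read-out and without baseline liver or spleen enlargement. A patient whose enlarged spleen fails to shrink misses PR for a different reason.
- **A single abnormal baseline feature is not clearly disqualifying.** The baseline-abnormality clause, and the separate PR condition in 11.227 for CT-only disease, both weaken that inference.

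All of this stands, and it limits the claim. It does not remove the conflict: no sentence gives the required count, and footnote 5 has no exception. The baseline clause does not clearly help the Rai I patient, whose lymphocytes were abnormal before therapy. Whether the literal score is stable disease or progression, the patient is a primary-endpoint failure.

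The objection that the size is uncertain also stands. Section 9.4 leaves lymphocytosis after daratumumab open, and the low end of the range costs Cohort 2 only about six points of power.

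**Conclusion.** The point holds as an unresolved contradiction inside the primary endpoint: Sections 11.22/11.221 and Table 11.4 footnote 5 against Section 11.0. It does not establish that affected patients will be scored stable disease. It establishes that the score depends on which text the assessor follows, and that the literal text biases the response rate downward.

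At 24 weeks on ibrutinib, roughly 3-22% of patients are affected. Under the literal reading, Cohort 2 power at a true 75% is about 0.85-0.30 instead of 0.91. Cohort 1 loses less. The range rests on the incidences in Section 1.2, which may not carry over after daratumumab, and on assumed exponential resolution and an assumed 30-70% without organomegaly. The contradiction depends on none of these. It should be settled before outcomes are read, since a later choice would be post hoc on the primary endpoint.

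**What to change.** 1. In Section 11.22 and Table 11.4 footnote 5, require at least two of 11.221-11.223 among the features that were abnormal at baseline and are assessable. If only one such feature remains, let that one suffice together with one of 11.224-11.226.
2. Reconcile 11.234 with 11.0 for endpoint scoring. Section 11.0 already says that treatment-related lymphocytosis does not represent progression, and 11.234 has no matching exemption. Without this, the first change would still miss many of the intended patients.
3. Report PR with lymphocytosis on a separate line of the response table.
4. Check how the study behind the historical 54% scored lymphocytosis, so that the 50% null and the endpoint use the same definition.
5. Reconcile end of Cycle 6 with end of Cycle 7 in Sections 16.311 and 16.11.

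The cost is a few sentences, one table line and one check of a source, with no change to sample size. The downside is that PR becomes slightly easier to reach in these patients. If the historical rate was scored strictly, the Cohort 2 type I error could exceed the stated 8%. The separate line makes that visible, and the check of the null shows whether the cut-off of 17 of 26 still fits.

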9.0 Ancillary Treatment/Supportive Care

9.1 Growth factors

Use of neutrophil growth factors (filgrastim and pegfilgrastim) or red blood cell growth factors (erythropoietin) is permitted per institutional policy and in accordance with the ASCO guidelines. They should be utilized as clinically warranted and following institutional policies and recommendations. Growth factors can be used during the treatment cycle as clinically indicated. The use of growth factors should follow published guidelines of the American Society of Clinical Oncology. Update of Recommendations for the Use of Hematopoietic Colony-Stimulating Factors: Evidence- Based, Clinical Practice Guidelines.

9.2 Supportive care:

Patients should receive full supportive care, including transfusions of blood and blood products, antibiotics, and antiemetics when appropriate. (A) Any blood transfusions administered must be irradiated blood products to reduce risk of transfusion- mediated graft versus host disease in CLL patients receiving T-cell suppressive therapy. Leukocyte reduction of all blood products for patients on protocol is also required. All blood products and concomitant medications such as antidiarrheals, analgesics, and/or antiemetics received from the first day of study treatment administration until 30 days after the final dose will be recorded in the medical records. (B) Antiemetics may be used at the discretion of the attending physician. (C) Prophylactic antibiotics and antifungals may be prescribed at the treating physicians' discretion and as clinically indicated, or as per the institutional guidelines. (D) Treatment for autoimmune cytopenias are permitted for <14 days at doses that do not exceed 100 mg per day of prednisone or equivalent. (E) Supportive medications in accordance with standard practice (such as for emesis, diarrhea, etc.) are permitted. (F) Short courses (≤ 14 days) of steroid treatment for non-cancer related medical reasons (e.g., joint inflammation, asthma exacerbation, rash, antiemetic use and infusion reactions) at doses that do not exceed 100mg per day of prednisone or equivalent are permitted.

9.3 Tumor Lysis Syndrome (TLS) prophylaxis and treatment:

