11.2 Definitions

The International Working Group criteria (IWCLL)⁷ will be used to assess response to therapy.

11.21 **COMPLETE RESPONSE (CR)** requires all of the following for a period of at least 2 months:

11.211 Absence of lymphadenopathy (e.g. lymph nodes >1.5 cm) by physical examination.

11.212 No hepatomegaly or splenomegaly by physical examination.

11.213 Absence of constitutional symptoms.

11.214 CBC demonstrating:

- Neutrophils >1500/uL.
- Platelets >100,000/uL (untransfused).
- Hemoglobin >11.0 gm/dL (untransfused).
- Peripheral blood lymphocytes <4000/uL.

Note: Patients who fulfill all criteria for a CR but who have a persistent anemia, thrombocytopenia, or neutropenia related to drug toxicity rather than residual CLL will be classified as **CR with incomplete marrow recovery (CRi)** according to the international criteria (Hallek, 2008).

11.215 Bone marrow aspirate and biopsy should be performed **within two months** after documentation of clinical and laboratory evidence of a complete response to document that a **complete response (CR)** has been achieved as per standard practice based upon IWCLL. The marrow sample should ideally be at least normocellular with <30% of nucleated cells being lymphocytes. Samples are to be analyzed by a pathologist and the presence or absence of nodules noted. Repeat bone marrow aspirate and biopsy are not necessary to document sustained CR.

NOTE: Patients who fulfill all criteria for a CR but who have hypocellular marrow will be classified as a **CR with incomplete marrow recovery (CRi)**.

In a subset of patients who are otherwise in a complete response, bone marrow nodules can be identified histologically. In such cases, special stains will be performed to determine whether such nodules represent "regenerative nodules" or residual "clonal nodules". The presence of regenerative nodules is consistent with CR while the presence of residual clonal nodules will be classified as an **nPR (nodular PR)** which is a sub-classification of PR. Per the PR criteria, patients must fulfill one or more of the blood count parameters (Section 11.224, 11.225, 11.226) but are not required to meet all 3 of these conditions.

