11.226 Hemoglobin $>11.0 \text{ gm/dl}$ or 50% increase over baseline without transfusions.

11.227 For patients whose only measurable disease at the time of enrollment is on CT scan, a CT scan demonstrating $> 50\%$ reduction of target nodes enlarged at baseline is required before classifying patients a PR.

11.23 **PROGRESSION (PD):** Patients will continue to receive protocol therapy unless they have evidence of disease progression according to the IWCLL criteria⁶ as evidenced by:

11.231 $\geq 50\%$ increase in the sum of the products of at least 2 lymph nodes on 2 consecutive determinations 2 weeks apart (at least one node must be ≥ 2 cm) or the appearance of new palpable lymph nodes >1.5 cm not due to a tumor flare. Enlargements or the appearance of new nodes due to a tumor flare do NOT qualify as progression.

11.232 $\geq 50\%$ increase in the size of the liver and/or spleen as determined by measurement below the respective costal margin on 2 consecutive determinations 2 weeks apart and with a minimum of a ≥ 2 cm increase in size from baseline; or appearance of hepatomegaly or splenomegaly which was not previously present at baseline and not due to a tumor flare.

11.233 Transformation to a more aggressive histology (e.g. Richter's transformation).

Note: If a patient develops DLBCL at any time, it will be considered disease progression. If the patient develops any other hematologic malignancy while on study, it will not be considered progressive disease.

11.234 $\geq 50\%$ increase in the absolute number of circulating lymphocytes NOT due to infection or tumor flare (taking as reference for progressive disease the smallest absolute lymphocyte count recorded since the treatment started). The absolute lymphocyte count must be at least 5000/mm³ to qualify as disease progression.

11.235 In the absence of progression as defined by 1, 2, 3, or 4 above, the presence of a ≥ 2 g/dl decrease in HGB, or $\geq 50\%$ decrease in platelet count, or absolute neutrophil count will NOT exclude a patient from continuing the study. Work-up of such decreases to exclude autoimmune hemolytic anemia, pure red cell aplasia, or idiopathic thrombocytopenic purpura (ITP) should be considered.

11.236 For patients who achieve a CR or nodular PR, progression will be defined as recurrence of circulating leukemia cell clone and an ALC >5000 or recurrence of adenopathy >1.5 cm not due to a tumor flare.

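### PR and nPR can be scored on a supported blood count: platelets carry no transfusion condition, unlike CR platelets in 11.214, and neutrophils and hemoglobin carry no growth-factor condition

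*Combined protocol and SAP*

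**What the plan says.** Section 11.22 builds PR from two parts. The disease part "requires the patient exhibits at least two of the features in Sections 11.221, 11.222, and 11.223 below (if abnormal prior to therapy"; these are the lymphocyte, nodal and liver/spleen criteria. The count part is met "as well as one or more of the remaining features (Sections 11.224, 11.225, 11.226) for at least 2 months". The three count lines are:

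- 11.224: "Neutrophils $>1500/\mu\text{l}$ or 50% improvement over baseline"
- 11.225: "Platelets $>100,000/\mu\text{l}$ or 50% increase over baseline"
- 11.226: hemoglobin above 11.0 g/dL, "or 50% increase over baseline without transfusions"

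For CR, 11.214 requires "Platelets >100,000/uL (untransfused") and hemoglobin also untransfused. Its neutrophil line is "Neutrophils >1500/uL" with no further condition. nPR uses the same one-of-three count rule as PR (11.215 and footnote 4 to Table 11.4).

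Section 9.1 permits filgrastim, pegfilgrastim and erythropoietin under institutional policy and ASCO guidance, and adds: "Growth factors can be used during the treatment cycle as clinically indicated". Section 9.2 permits transfusion where appropriate. Neither section refers to response assessment. Section 16.311 counts PR and nPR as successes and has no rule for supported counts.

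**The concern.** The protocol treats the same measurement differently by response category without giving a reason. A transfused platelet count is barred from CR in 11.214 but not from PR or nPR. Hemoglobin is protected against transfusion in both, while neutrophils are protected against growth factors in neither.

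Two patients with the same nodal and splenic shrinkage, and all three counts below the criteria without support, can then be scored differently. The one on G-CSF with neutrophils above 1500 is a PR; the one not on G-CSF is SD. The difference is a concomitant medication, yet it decides whether the patient is a primary-endpoint success. The trial is single-arm within each cohort, so no comparator would absorb the effect. In Cohort 1 the decision turns on 3 responders out of 22. Without a rule set in advance, such cases would be settled one at a time with treatment known.

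**Working it through.** **1. The criteria side by side**

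| Count | CR (11.214) | PR (11.224–11.226) | Table 11.4, PR and nPR |
|---|---|---|---|
| Neutrophils | no growth-factor condition | none | none |
| Platelets | untransfused | no condition | no condition |
| Hemoglobin | untransfused; no erythropoietin condition | without transfusion; no erythropoietin condition | same as PR |

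The platelet row of Table 11.4 carries no transfusion condition in the CR and CCR columns either, so there the table also departs from 11.214. The placement of the clause in 11.226 leaves open whether it covers the 11.0 g/dL threshold or only the 50% increase.

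**2. Who is affected**

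Only a patient who (a) meets two disease features, (b) meets none of the three counts unsupported, and (c) meets at least one with support. Section 3.17 admits neutrophils from 1000, platelets from 50,000 and hemoglobin from 7, all below the fixed response thresholds, so (b) is possible at entry. Neutropenia on treatment is also foreseeable: section 1.2 reports grade 3 or 4 neutropenia in 16.4% of the ibrutinib arm of the cited randomized phase 3 CLL study. Neither figure says how often all three counts fail together.

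The requirement of at least 2 months makes platelet transfusion alone an unlikely route. Repeated G-CSF is more plausible. The text does not say how many counts must establish the 2 months.

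**3. The plan's own operating characteristics**

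Formula: P(X ≥ r), with X binomial (n, p).

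- Cohort 1 (16.211–16.212), n = 22, r = 3: 0.0948 at p = 0.05 and 0.846 at p = 0.20. The plan states 0.09 and 0.85.
- Cohort 2 (16.221–16.222), n = 26, r = 17: 0.0843 at p = 0.50 and 0.909 at p = 0.75. The plan states 0.08 and 0.91.

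Both reproduce.

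**4. Sensitivity**

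Let f be the share of true non-responders scored PR only because of a supported count. The documents give no value, so f is an assumption. The apparent success rate at the null is p0 + (1 − p0)f.

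| f | Cohort 1 rate | Cohort 1 P(promising) | Cohort 2 rate | Cohort 2 P(promising) |
|---|---|---|---|---|
| 0 | 0.0500 | 0.095 | 0.500 | 0.084 |
| 1% | 0.0595 | 0.140 | 0.505 | 0.093 |
| 2% | 0.0690 | 0.191 | 0.510 | 0.101 |
| 5% | 0.0975 | 0.364 | 0.525 | 0.131 |

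In expected patients, f = 1%, 2% and 5% means 22 × 0.95 × f = 0.21, 0.42 and 1.05 in Cohort 1, and 26 × 0.50 × f = 0.13, 0.26 and 0.65 in Cohort 2. The 5% row therefore supposes about one such patient in Cohort 1.

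**5. One certain false success in Cohort 1**

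If exactly one of the 22 is a false success and the other 21 respond at 5%, P(X ≥ 2 | 21, 0.05) = 0.283. If such a patient is present only with probability q, the chance is 0.0948 + q(0.283 − 0.0948): 0.104 at q = 5%, 0.114 at 10% and 0.132 at 20%. Again, q is an assumption.

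**The case against.** The strongest reply is that the count part is not declared to be a test of marrow recovery, and that the protocol accepts responders without recovery. CRi covers patients who otherwise meet CR but have lasting drug-related cytopenia, and 16.311 counts CRi as a success. Section 8.0 notes that falling counts may come from treatment or from disease. A patient with real nodal and splenic shrinkage whose neutropenia is drug-induced has arguably responded, and a strict exclusion would score that patient SD. This stands as a cost of the change, because it creates an error in the opposite direction. It does not explain why platelets are treated differently in CR and PR.

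A reader might infer that supportive care alone can make a responder, or that it may be given without restriction. The documents support neither. Two disease features must still be met, and sections 9.1 and 9.2 tie use to clinical need and, for growth factors, to guidelines. What is missing is any link between that use and scoring.

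Section 11.2 also says that IWCLL criteria will be used, and the cited source may limit supported counts. That cannot be checked from these documents. The written-out criteria are what an assessor will apply, and they are inconsistent as they stand.

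Finally, anyone with one adequate unsupported count is unaffected. That stands, and it is why the effect is probably small.

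**Conclusion.** The inconsistency is real. It lies in the stated rule and is more than an omitted detail: the PR and nPR criteria can turn a supported count into a primary-endpoint success. Platelets are the clearest textual conflict; neutrophils on repeated G-CSF are the likelier practical case.

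The size is unknown. Cohort 1 is the more exposed because of its low cut-off. The probabilities for f of 1% to 5% are illustrations that rest on an assumed misclassification rate; they are not forecasts. A reader might take the 0.283 figure as the trial's false-positive rate. It is not: it assumes that one false success has already occurred, and with a modest chance of such a patient the rate stays much nearer 0.095. The point justifies a wording change before analysis. It gives no reason to doubt the sample sizes or the decision cut-offs.

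**What to change.** In 11.224–11.226 and the PR and nPR count rows of Table 11.4:

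- require the qualifying platelet or hemoglobin value to be free of transfusion, and the qualifying neutrophil or hemoglobin value to be free of growth-factor support, within one look-back window fixed before analysis;
- apply that window to the counts that establish the 2-month duration, and say which counts those are;
- make clear that the hemoglobin condition covers both the threshold and the percentage increase.

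Align the neutrophil line of 11.214, bring the CR and CCR entries in the table's platelet row into line with 11.214, and leave the CRi provision as it is.

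Collect transfusion and growth-factor dates with each response assessment. Section 9.2 places blood products and concomitant medications in the medical records, and Appendix V asks that growth-factor use be documented. Neither says that these data reach the response assessor, so a small addition to the case report form may be needed.

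The change affects scoring only; supportive care stays as permitted. The cost is that a few responses may be dated later or scored SD, including some in patients with drug-related cytopenia, so the reported response rate may be slightly lower.
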